13.4. Monitoring and Recording of Adverse Events

AE data collection will begin after a subject signs the ICF and will continue until completion of the safety follow-up visit (Visit 29) or 28 days after the final dose of study drug. Any AE or SAE having an onset after the safety follow-up visit will not be collected or reported unless the investigator feels that the event may be related to the study drug.

Subjects will be instructed by the investigator or designee to report the occurrence of any AE. All volunteered, elicited, and observed AEs are to be recorded on the AE eCRFs.

The investigator will assess all AEs regarding any causal relationship to the study drug (see [Section 13.3](#)), the intensity (severity) of the event, action taken, and subject outcome.

The following criteria should be used to guide the assessment of intensity (severity):

- **Mild:** Causes awareness of sign or symptom, but is easily tolerated; does not interfere with usual activities
- **Moderate:** Causes discomfort enough to interfere with usual activities
- **Severe:** Is incapacitating; results in inability to work or perform usual activities

All AEs will be followed until resolution, until deemed stable by the investigator, or until the subject is deemed by the investigator to be lost to follow-up.

For clinical study safety reporting purposes, the most recent version of the Investigator's Brochure will be used as the reference document to designate event expectedness.

Withdrawal from the study as a result of an AE and any therapeutic measures that are taken shall be at the discretion of the investigator. If a subject withdraws from the study for any reason, any ongoing AEs will be followed until resolution, until deemed stable by the investigator, or until the subject is deemed by the investigator to be lost to follow-up.

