3.2.2. Follow-up Safety Population

Follow-up Safety Population will be defined with respect to the 5 half-lives of the product as subjects in the Safety Population and met any of the following criteria:

- Completed at least one follow-up visit after >7 days of the last dose of ALKS 3831
- Reported at least one AE reported after >7 days of the last dose of ALKS 3831

This population will be used to analyze the AEs in the safety follow-up period.

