3.2.3. Post-discontinuation Safety Population

Post-discontinuation Safety Population will be defined as subjects in the Safety Population and met any of the following criteria:

- Completed at least one follow-up visit after >2 day within 16 days of the last dose of ALKS 3831
- Reported at least one AE reported after >2 day after the last dose of ALKS 3831

AE to evaluate potential for drug withdrawal and dependence emerging following discontinuation of ALKS 3831 will be assessed for this population, during the period of >2 days to 16 days after the last dose of drug for subjects with at least 4 weeks study drug exposure.

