3.9. Safety Analysis

3.9.1. Adverse Events

Incidence of treatment emergent AEs (TEAEs) will be analyzed as a safety endpoint. Adverse events will be coded by System Organ Class and Preferred Term using the Medical Dictionary for Regulatory Activities (MedDRA[®]) Version 21.0 or higher. The verbatim term will be included in the AE listings.

An AE (coded by preferred term) will be considered as a TEAE if the event is newly occurring or worsening on or after the date of first dose of study drug and within 7 days after the last dose of study drug in this study.

An overview table, including number of subjects with TEAEs, AEs leading to treatment discontinuation, study drug related TEAEs, and SAEs will be provided.

The incidence (number and percentage) of subjects reporting TEAEs during the treatment period will be presented for the following categories:

- System organ class and preferred term
- Preferred term, and including the following subset:
 - TEAEs experienced by $\geq 2\%$ of subjects (in any group)
- System organ class, preferred term, and severity
- System organ class, preferred term for severe TEAEs

- System organ class, preferred term, and relationship
- System organ class, preferred term for study drug related TEAEs

If the same preferred term occurred more than once for the same subject, the subject will be counted only once for that preferred term using the most severe and most related occurrence for the summarization by severity and by relationship to the study drug.

In addition, the number and percentage of subjects reporting AEs during the safety follow-up period will be tabulated by the system organ class and preferred term.

Subgroup analysis by age (<40 years vs \geq 40 years), sex (Female vs Male) and race (Black or African American, White, and Other) will be performed for TEAEs during the treatment period by preferred term.

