3.9.1.3.2. Analysis of Withdrawal and Dependence

Adverse events with an onset date within 2 weeks (>2 to ≤ 16 days) after the last dose of the study drug in those subjects who have received at least 4 weeks of study drug will be included in the evaluation of the potential for withdrawal and dependence. The selection of AEs per subset will be based on the preferred terms from Customized MedDRA queries (CMQs).

The number and percentage of subjects with such AEs will be summarized in the Post-discontinuation Safety Populations by preferred term for subjects with a duration of study drug exposure ≥ 4 weeks.

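### Entry to the two post-treatment AE populations (SAP 3.2.2 and 3.2.3) depends on whether an AE was reported, and 3.2.3 limits the visit, but not the AE, to 16 days

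*SAP*

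**What the plan says.** Below, Day n means n days after the last dose.

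**Follow-up Safety Population (SAP 3.2.2).** A Safety Population subject enters by meeting either of two criteria. One is a follow-up visit after Day 7. The other is "Reported at least one AE reported after >7 days of the last dose of ALKS 3831". This is the population for the follow-up AE table in SAP 3.9.1, where "the number and percentage of subjects reporting AEs during the safety follow-up period will be tabulated by the system organ class and preferred term".

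**Post-discontinuation Safety Population (SAP 3.2.3).** Again either criterion is enough. The visit criterion is "Completed at least one follow-up visit after >2 day within 16 days of the last dose of ALKS 3831". The AE criterion is "Reported at least one AE reported after >2 day after the last dose of ALKS 3831". The analysis itself is confined to AEs "during the period of >2 days to 16 days after the last dose of drug", in subjects with at least 4 weeks of exposure. SAP 3.9.1.3.2 repeats that onset window, selects the AEs by custom MedDRA queries, and states: "The number and percentage of subjects with such AEs will be summarized in the Post-discontinuation Safety Populations by preferred term".

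**AE collection (Protocol 13.4).** Collection "will continue until completion of the safety follow-up visit (Visit 29) or 28 days after the final dose of study drug". Protocol 7.3 and 8.2 also ask subjects who stop early to attend monthly visits at which AEs are recorded.

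SAP 3.2.1 sends these analyses to these two populations. The rest of the SAP gives no other denominator for the two tables.

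**The concern.** A percentage of subjects with an AE is an incidence only if subjects are counted because they were observed, whatever was found. Here, of two subjects with no qualifying visit, the one with a reported AE is counted and the one without is not.

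SAP 3.2.3 has a second fault. The visit must fall by Day 16 and the numerator stops at Day 16, but the admitting AE may start later and need not be a withdrawal or dependence term. A subject whose only AE starts on Day 20 is in the denominator and cannot be an event. Conversely, an AE-free subject whose first follow-up visit falls on Day 17 is dropped, while the same subject with an AE stays in.

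The stake is how two descriptive tables are read. One of them is the SAP's dedicated summary of withdrawal and dependence, for a product containing an opioid modulator. A reader will take its percentage as the incidence among subjects followed after stopping, and it is not that.

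**Working it through.** The plan states no size or rate for either population, so there is no figure to reproduce. The rates below are assumptions that show direction and range.

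**1. Follow-up table, any AE.** Let v be the share with a qualifying visit, p the AE risk (taken as equal with and without a visit), and c the share of non-attenders' AEs that reach the database. The rule gives

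rate = [v·p + (1−v)·p·c] / [v + (1−v)·p·c].

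With p = 10%, the visit-based rate is 10.0%. For 150 subjects at 80% attendance (120 with a visit, 30 without):

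- c = 10%: (12 + 0.3)/(120 + 0.3) = 10.2%
- c = 50%: (12 + 1.5)/(120 + 1.5) = 11.1%
- c = 100%: (12 + 3)/(120 + 3) = 12.2%

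| Attendance | c = 10% | c = 50% | c = 100% |
|---|---|---|---|
| 95% | 10.05% | 10.2% | 10.5% |
| 80% | 10.2% | 11.1% | 12.2% |
| 60% | 10.6% | 12.9% | 15.6% |

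Subjects admitted only by an AE have an any-AE rate of 100% by construction, so this figure cannot fall below the visit-based rate if the admitting AEs are counted.

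**2. Follow-up table, one preferred term.** Each AE-only entrant enlarges the denominator of every row, but the numerator only of that subject's own terms. Take a term at 2.0% among attenders (2.4 of 120) and 3 AE-only entrants. If none has the term, the row is 2.4/123 = 1.95%. If they have it in the same mix as attenders (0.6 of the 3), it is 3.0/123 = 2.4%.

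**3. Withdrawal/dependence, any query term.** The reported rate is a weighted average of the visit-based rate and the share s of AE-only entrants with a counted event. It rises only if s exceeds the visit-based rate. Assume a 5% risk of a query-term AE in the window and a separate 10% risk of some other AE that admits a subject but is not counted. At 80% with a qualifying visit:

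- All non-attenders' AEs recorded, s = 5/15 = 33%: (6 + 1.5)/(120 + 4.5) = 6.0%
- No AE-only entrant has a counted event, s = 0: 6/(120 + 3) = 4.9%

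At 60% the same two cases give 7.5/99 = 7.6% and 4.5/96 = 4.7%.

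**4. Can an observed subject miss the Day 16 limit?** For early terminators, Protocol 7.3 and 8.2 time the first follow-up visit 2 weeks after the ET visit, with a window of ±2 days. It therefore falls on Day (lag + 12) to (lag + 16), where lag is the number of days from last dose to ET visit. Lag 0 gives Days 12 to 16, lag 1 gives Days 13 to 17, and lag 2 gives Days 14 to 18. From a lag of 1 day, which bedtime dosing (Protocol 9.1) makes ordinary, a visit within its window can fail.

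The effect depends on the share f of visits that fall too late. With full attendance and the risks in step 3, rate = 0.05/[(1−f) + 0.15f]. This is 5.2% at f = 5% and 6.0% at f = 20%.

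**The case against.** The best defence is that a safety extension should keep every AE reported after treatment, and the AE route does so. Restricting to observed subjects can understate risk. Suppose risk is 10% in 120 attenders and 20% in 30 non-attenders, so the true rate is 18/150 = 12.0%. Visits alone give 12/120 = 10.0%. The SAP rule gives (12 + 3)/(120 + 3) = 12.2% if half of the non-attenders' AEs are recorded. That agreement comes from two errors cancelling: with 10% recorded the rule gives 12.6/120.6 = 10.4%, and with all recorded 18/126 = 14.3%. The point stands as a reason to report AEs in unobserved subjects, but not to place them in a denominator that excludes their AE-free counterparts.

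Several stronger readings are tempting, and the documents do not support them:

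- **That both tables overstate incidence.** Only the follow-up any-AE figure has a fixed direction, and the SAP tabulates by organ class and preferred term. Steps 2 and 3 show movement both ways.
- **That the distortion is large.** The largest values pair poor attendance with complete recording of non-attenders' AEs. Without a visit, an AE is recorded only through some other contact, so that pairing is unlikely; at 10% recorded the effect is at most 0.6 points in the table above.
- **That the Day 16 limit alone moves 5% to 6%.** That needs one visit in five to fall on the last allowed day at a 1-day lag. The documents give no distribution of visit dates, the nominal visit is then Day 15, which qualifies, and Protocol 7.3 wants the ET visit soon after the last dose.
- **That a signal could be lost.** Counts appear beside the percentages, all events are listed, and AEs on Days 3 to 7 are also in the TEAE tables on the Safety Population (SAP 3.9.1).

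The dataset and programming specifications are separate documents (SAP 6 and 8). They might narrow the rule, but the SAP text does not.

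**Conclusion.** The point holds on the wording. Both denominators admit subjects without a qualifying visit only through a reported AE, and in 3.2.3 the AE criterion is wider in term and time than the numerator it serves. The resulting percentages are not incidences in a group defined by observation.

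The direction is fixed only for the follow-up any-AE figure, and only if the admitting AEs are counted. The size cannot be stated from the documents. It depends on attendance, on how many AEs are recorded without a visit, and on the mix of terms, and it may be negligible. Severity is minor to moderate: the tables are descriptive and detection of events is not affected.

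**What to change.** Define both populations by observation regardless of AE status, and delete the AE-only route.

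- **SAP 3.2.2:** Safety Population subjects with at least one follow-up visit, or documented contact at which AEs were asked about, more than 7 days after the last dose.
- **SAP 3.2.3:** Safety Population subjects with at least 4 weeks of exposure who did not roll over to ALK3831-A308, and who had at least one visit of any type, or documented contact at which AEs were asked about, more than 2 days after the last dose. Apply one rule to ET visits, follow-up visits and telephone contacts, with no 16-day upper limit on the visit or contact.
- **Numerator for 3.9.1.3.2:** keep onset >2 to ≤16 days.
- **Both tables:** give AEs in subjects with no qualifying observation as a separate count beside the table. Footnote that the percentage describes observed subjects; for 3.2.3, add that some were not observed through Day 16.

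The cost is SAP text and two population flags. Visits and AEs are already recorded. Protocol 7.3 requires telephone data to be kept in the subject's record but does not say that contact dates are on the eCRF, so some may need retrieval.

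The downside is that the percentage can understate risk if unobserved subjects fare worse. The separate count discloses this, and telephone contacts reduce it: in the unequal-risk example, reaching half of the non-attenders gives 15/135 = 11.1% against 10.0% from visits alone.

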3.3. Disposition

The number and percentage of subjects completing or prematurely discontinuing the study including reasons for discontinuation will be summarized for the following:

- Subjects who enrolled in the study

- Subjects in the Safety Population
- Subjects who completed the treatment period
- Subjects who discontinued treatment along with reason for discontinuation (as indicated in case report form)

3.4. Protocol Deviation

Subjects with major protocol deviations in the following categories will be summarized. A supportive listing will be provided as well.

- Did not meet the study entry criteria
- Received prohibited medications
- Lack of adherence with study medication, as defined by subjects taking less than 70% of protocol specified amount of study medication
- Dosing error

3.5. Demographics and Baseline Characteristics

Demographics and baseline characteristics such as sex, age, race, ethnicity, weight, and body mass index (BMI) will be summarized for the Safety Population and for the subset of subjects who participated in the patient voice substudy.

3.6. Prior and Concomitant Medication

Prior medications will be defined as medications taken prior to the first dose of study drug in ALK3831-A304 study. Concomitant medications will be defined as medications taken on or after the first dose of study drug in ALK3831-A304 study. All medications will be coded using the World Health Organization WHO-DD Enhanced + Herbal (version: March 2016) or higher.

Concomitant medications taken during the treatment period will be summarized by the preferred drug name. All reported medications (including those initiated after the last dose of study medication) will be included in the listing. For the summary table, if a subject has taken a concomitant medication more than once, the subject will be counted only once for that medication.

3.7. Treatment Adherence Rate and Extent of Exposure to Study Drug

3.7.1. Treatment Adherence Rate

Treatment adherence to the daily dosing schedule during treatment period will be summarized. Treatment adherence will be calculated as follows:

$$100 \times \frac{\text{Total tablets dispensed} - \text{total tablets returned} - \text{total tablets lost}}{\text{Total tablets scheduled to be taken}}$$

3.7.2. Extent of Exposure to Study Drug

Duration of exposure to study drug (ALKS 3831) is defined as the number of days from the date of the first dose of study drug of this study (ALK3831-A304) to the date of the last dose of study drug, inclusive (ie, last dose date – first dose date + 1 day). Duration of study drug administration will be summarized.

The overall mean and modal dose of olanzapine will be summarized

3.8. Efficacy Analyses

3.8.1. General Considerations

In general, continuous and categorical endpoints will be summarized using descriptive statistics based on observed data.

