7.3. Subject Withdrawal

A subject may be discontinued from the study at any time if the subject, investigator, or the sponsor determines that it is not in the best interest of the subject to continue participation. If a subject has an absolute neutrophil count (ANC) $< 1.0 \times 10^3$ per μL or glycosylated hemoglobin (HbA1c) $\geq 6.5\%$ at any time during this extension study, the subject will be discontinued from the study. Other reasons for discontinuation include the following:

- Adverse Event (AE)
- Lack of Efficacy
- Lost to follow-up
- Withdrawal by subject
- Protocol Deviation (non-compliance with study drug or study procedures)
- Pregnancy
- Study terminated by sponsor
- Other

If a subject withdraws from the study for any reason, he or she will be asked to return to the clinic for an early termination (ET) visit. The ET visit should be scheduled as close as possible to the subject's last dose and will mimic the assessments scheduled to be conducted at the end of treatment (EOT) visit (Visit 27, [Table 3](#)). Following the ET visit, subjects who discontinue study drug but are willing to come in for further assessments will be asked to complete 2 safety follow-up visits 2 and 4 weeks after the ET visit (same assessments as Visits 28 and 29 in [Table 3](#)). They will then be asked to return to the study center for monthly visits according to the schedule outlined in [Table 3](#) for follow-up weight assessments, adverse events, and documentation of any new antipsychotic medications the subject is taking.

Following ET, any ongoing AEs will be followed until resolution, or until deemed stable by the investigator, or until the subject is deemed by the investigator to be lost to follow-up. If, in the opinion of the investigator, it is necessary to monitor a subject beyond the safety follow-up visit, the follow-up period may be extended as necessary. In such instances, the sponsor and the investigator will agree to an acceptable follow-up schedule.

In the event that a subject chooses to withdraw from the study, the investigator should make a reasonable effort to ascertain the reason(s) for withdrawal, while fully respecting the subject's rights. If the subject fails or refuses to return to the study center, an attempt must be made to contact the subject by telephone in order to assess as many safety and efficacy parameters as possible. All data collected over the telephone must be documented and kept in the subject's record.

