3.8.2. Efficacy Analysis

The following endpoints will be used to evaluate durability of treatment effect:

- Change from baseline in PANSS total score, and subscales (positive, negative, and general psychopathology subscales) by visit
- Change from baseline in CGI-S by visit
- Shift analysis in CGI-S
- Time to treatment discontinuation

Summary statistics will be provided for all continuous endpoints based on observed data.

Change from current (A304) and precedent (A303) study baseline in PANSS total score and subscales will be summarized for the subset of subjects who participated in the patient voice substudy.

CGI-S response will be categorized into the categories summarized in [Table 1](#). The number and percentage of subjects in each category and with shifts from baseline will be summarized based on the observed data by descriptive statistics at 4, 12, 24 and 52 weeks. The shift categories are summarized in [Table 2](#).

Time to treatment discontinuation will be analyzed using the Kaplan-Meier method. Both all-cause discontinuation and discontinuation due to AE will be summarized. For prematurely discontinued subjects (all-cause or due to AE), time to discontinuation is defined as time from the date of first dose of study drug to the date of last dose of study drug. Other subjects will be censored at the last dose of the study drug.

Table 1: Definition of CGI-S Categories

Response Category	CGI-S Score
Markedly to Extremely Ill	≥ 5

Response Category	CGI-S Score
Moderately Ill	4
Normal to Mildly Ill	≤3

Table 2: Shift Categories for CGI-S response

Shift from Baseline Category for CGI-S Response	
Baseline Category	Shift Category
Markedly to Extremely Ill	No change ≥1 level improvement 2 level improvement
Moderately Ill	No change 1 level improvement 1 level worsening
Normal to Mildly Ill	No change ≥1 level worsening 2 level worsening

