6.1. Analysis Visit Windows

Scheduled analysis visits are visits at scheduled timepoints as specified in the protocol ([Table 3 Schedule of Visits and Assessments](#)).

Scheduled analysis visits during the study period will be the same as the nominal visits collected in eCRF. There will be one valid value of assessment kept for each scheduled analysis visit in summary/analysis statistics.

Unscheduled visits are visits with data not collected on the scheduled time point. Unscheduled visits will not be used for by-visit summary/analysis statistics, unless specified otherwise.

All unscheduled visits as collected in eCRF will be included in listings.

Last postbaseline values are defined as the last valid postbaseline values collected for each subject during the treatment period.

An early termination (ET) visit during the on-treatment period can be mapped to a scheduled visit, if there is no valid value already at that visit. Visit windows are defined in [Table 11](#) and [Table 12](#). An ET visit that is not mapped will not be summarized in the tables or figures, but will be included in the listing.

Table 11: Visit Window for All Efficacy and Safety Assessments Excluding PANSS

Analysis Visit to be Mapped to	Target Study Week	Target Visit Day ^a	Visit Window
Visit 1	Week 0	Day 1	1
Visit 2	Week 2	Day 15	[2, 21]
Visit 3	Week 4	Day 29	[22, 35]
Visit 4	Week 6	Day 43	[36, 49]
Visit 5	Week 8	Day 57	[50, 70]
Visit 7	Week 12	Day 85	[71, 98]

Analysis Visit to be Mapped to	Target Study Week	Target Visit Day ^a	Visit Window
Visit 9	Week 16	Day 113	[99, 126]
Visit 11	Week 20	Day 141	[127, 154]
Visit 13	Week 24	Day 169	[155, 182]
Visit 15	Week 28	Day 197	[183, 210]
Visit 17	Week 32	Day 225	[211, 238]
Visit 19	Week 36	Day 253	[239, 266]
Visit 21	Week 40	Day 281	[267, 294]
Visit 23	Week 44	Day 309	[295, 322]
Visit 25	Week 48	Day 337	[323, 350]
Visit 27	Week 52	Day 365	[351, 371]

^a Visit Day is calculated as date of visit – date of the first dose of study drug + 1 day.

Table 12: Visit Window for PANSS Assessments

Analysis Visit to be Mapped to	Target Study Week	Target Visit Day	Visit Window
Visit 2	Week 2	Day 15	[2, 21]
Visit 3	Week 4	Day 29	[22, 42]
Visit 5	Week 8	Day 57	[43, 70]
Visit 7	Week 12	Day 85	[71, 126]
Visit 13	Week 24	Day 169	[127, 210]
Visit 19	Week 36	Day 253	[211, 308]
Visit 27	Week 52	Day 365	[309, 371]

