7. GENERAL STATISTICAL METHODOLOGY

In general, summary statistics (n, mean, SD, median, minimum, and maximum for continuous variables, and number and percentage of subjects in each category for categorical variables) will be provided by treatment sequence and overall. All summary tables will be based on observed data, and missing values will not be imputed. Measurements collected from unscheduled visits or repeated assessments will not be included in the by-visit summary tables or figures, but will be included in the analyses for the PCS postbaseline values, and subject listings. Source data for the summary tables will be presented as subject data listings.

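### PANSS and CGI-S summaries are observed-case with no supporting summary, and an early-termination score is only listed when its visit window already holds a value

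*SAP*

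**What the plan says.** - **Data basis.** Under SAP 3.8.1, efficacy endpoints of both kinds, continuous and categorical, are in general to be "summarized using descriptive statistics based on observed data". SAP 7 repeats it for the whole report: "All summary tables will be based on observed data, and missing values will not be imputed".
- **Durability endpoints.** Protocol 14.5 lists change in PANSS, change in CGI-S and time to discontinuation. SAP 3.8.2 keeps these and adds "Shift analysis in CGI-S", tabulated from observed data at Weeks 4, 12, 24 and 52.
- **Discontinuation.** "Time to treatment discontinuation will be analyzed using the Kaplan-Meier method", and "Both all-cause discontinuation and discontinuation due to AE will be summarized". Subjects without the event in question are censored at last dose. SAP 3.3 tabulates reasons for discontinuation, and Protocol 7.3 lists "Lack of Efficacy" among them.
- **ET visit.** Under Protocol 7.3 and 8.2, subjects who leave are asked to attend an ET visit with the Visit 27 assessments, which include PANSS and CGI-S. The later monthly visits collect weight, adverse events and new antipsychotics, but neither scale.
- **ET mapping.** Under SAP 6.1 an on-treatment ET value can fill a scheduled visit only if that visit has no valid value. Otherwise it appears in the listing alone.
- **Last value.** SAP 6.1: "Last postbaseline values are defined as the last valid postbaseline values collected for each subject during the treatment period". No PANSS or CGI-S summary uses this definition. By contrast, SAP 3.9.3.3 gives ECG parameters a summary at the end of the treatment period.

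**The concern.** Lack of efficacy is a recorded reason for leaving, so whether a score is missing at Week 52 can depend on how the subject was doing. If subjects who lose response leave sooner, the mean in those who remain can stay flat while effect is being lost in the enrolled group. The CGI-S shift table has the same limit because it too uses observed data.

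The ET rule adds to this. The score taken at leaving bears most directly on whether effect was lost. It is collected, but it can then be kept out of every table, and no later visit measures the scale again. What is at stake is whether a reader can tell durable effect from selective retention.

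**Working it through.** The documents give no dropout rate, PANSS standard deviation or expected change, so there is no planned figure to reproduce. The planned size of about 540 is the estimated maximum roll-over from the antecedent study, not a calculation. Two checks are possible.

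**1. How often is an ET score left out of the tables?**

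Inputs: the PANSS windows in SAP Table 12, the windows for other assessments in SAP Table 11, and the CGI-S schedule in Protocol Table 3. Assume that earlier visits took place on their target days and that the ET visit falls in the on-treatment period. An ET score is then unmapped on every day of a window after its target day. Possible ET days are 2 to 364, which is 363 days.

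| PANSS window | Target day | Days on which ET is unmapped |
|---|---|---|
| 2–21 | 15 | 16–21: 6 |
| 22–42 | 29 | 30–42: 13 |
| 43–70 | 57 | 58–70: 13 |
| 71–126 | 85 | 86–126: 41 |
| 127–210 | 169 | 170–210: 41 |
| 211–308 | 253 | 254–308: 55 |
| 309–371 | 365 | none before day 365: 0 |

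- PANSS: 6 + 13 + 13 + 41 + 41 + 55 = 169, and 169/363 = 46.6%.
- CGI-S: 6 (Visit 2) + 6 (Visit 3) + 13 (Visit 5) + 10 × 13 (Visits 7, 9, ..., 25) = 155, and 155/363 = 42.7%. CGI-S is not scheduled at Visit 4, so an ET score in that window is always mapped.
- Shifting all visits by the allowed 2 days gives 157 to 182 days for PANSS (43.3% to 50.1%) and 129 to 182 for CGI-S (35.5% to 50.1%).

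On the remaining days the ET score enters once, at the mapped visit, and the subject is absent from later visits. An ET score can count at Week 52 only from day 309 for PANSS or day 351 for CGI-S.

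**2. How far could the Week 52 mean be off?**

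Let d be the share with no Week 52 value, S the mean change in subjects with one, and L the mean change in those without, measured at their last score. Higher PANSS is worse.

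- All-subject mean = (1 − d)S + dL
- Observed mean minus all-subject mean = S − (1 − d)S − dL = −d(L − S)

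Both d and L − S are assumed, for illustration only:

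- d = 20%, L − S = 5: 0.2 × 5 = 1.0 point too favourable
- d = 30%, L − S = 10: 0.3 × 10 = 3.0 points too favourable
- d = 40%, L − S = 15: 0.4 × 15 = 6.0 points too favourable
- L − S = 0: no difference at any d
- L − S = −5, d = 20% to 40%: 1.0 to 2.0 points too unfavourable

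With 540 enrolled, d of 20% to 40% leaves 432 to 324 subjects at Week 52.

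**The case against.** A reader might infer that durability rests on observed means alone, that subjects who worsen and leave vanish from the report, and that stability is therefore overstated. The documents do not support that reading.

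- Time to discontinuation is itself a listed durability endpoint, and every lack-of-efficacy withdrawal is an event in the all-cause curve.
- Leavers count at the visits they attended and in disposition by reason. The falling n is shown by visit, some ET scores are mapped, and all source data are listed.
- Week 52 is not confined to completers, since a late ET score can map there.
- Some withdrawals need not track symptoms, such as pregnancy or the neutrophil and HbA1c rules in Protocol 7.3. The direction of any distortion is not known.
- Hospitalisation for behavioural worsening is reported as a serious adverse event (Protocol 13.2). If it leads to discontinuation recorded as due to AE, it falls in the AE curve, and a lack-of-efficacy curve would miss it.
- The study is open-label and descriptive, with safety and tolerability as its only stated objective. A last-value summary or a mixed model replaces one missing-data assumption with another, and neither creates a control group.

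All of this stands, and it limits the weight of the point. It does not close the gap. The all-cause curve mixes loss of effect with unrelated reasons. The AE curve censors lack-of-efficacy leavers at last dose. Disposition gives counts without timing or scores.

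**Conclusion.** The point holds as a limit on interpretation, not as a demonstrated bias. The planned tables and figures do not reliably show how symptomatic subjects were when they left, or when lack-of-efficacy withdrawals occurred. A stable Week 52 PANSS or CGI-S mean would therefore fit both durable effect and selective retention.

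The 46.6% and 42.7% are exact for the stated windows, given on-target visits and an on-treatment ET visit. The share of subjects affected depends on when they leave, which the documents do not predict. The 1 to 6 points depend wholly on assumed inputs and could be zero or reversed. The all-subject mean in that comparison combines last scores from different times with Week 52 scores, so it is a yardstick and not a true Week 52 value. This is a cheap improvement to a descriptive durability aim.

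**What to change.** Keep the observed-case tables and add to SAP 3.8.2:

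1. Change from baseline to last on-treatment value for PANSS total, PANSS subscales and CGI-S, using the SAP 6.1 last postbaseline definition and shown by completion status. State that ET scores count even when not mapped to a visit. Protocol 7.3 asks for the ET visit as close as possible to the last dose, so also state whether an ET score taken shortly after that dose falls within the treatment period.
2. A cumulative-incidence (or Kaplan-Meier) curve for discontinuation due to lack of efficacy, beside the all-cause and AE curves and not in place of them.
3. Optionally, a mixed model for repeated measures giving a Week 52 estimate from all postbaseline visits.

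Items 1 and 2 use data already collected. The cost is a few table rows and one figure. The last-value summary mixes time points, so it supplements the Week 52 mean and does not replace it. The added result may be less favourable than the observed mean.
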